#### **1.4.2 Risks**

Empagliflozin is investigational agent. Table 1.4.2: 1 displays the anticipated side effects of the study drugs, based on the mechanism of action, observed clinical data from ongoing studies, and published clinical data.

Table 1.4.2: 1 Potential risks, their rationale, and mitigation strategy

Potential risks of clinical relevance for this trial	Summary of data, rationale for the risk	Mitigation strategy
Investigational Medicinal Product: Empagliflozin		
Hypersensitivity and allergic reactions	As with all drugs, the potential for hypersensitivity and allergic reactions has to be taken into consideration.	Investigators will monitor the patients both clinically and by laboratory testing
Unexpected adverse events		
Hyperglycemia	One third (33.3%) of patients will receive placebo and these patients thus have a higher probability of treatment failure, i.e., of increase in FPG and HbA 1c	Appropriate inclusion/exclusion criteria of HbA 1c and FPG value and criteria for rescue therapy and patient discontinuation will ensure an adequate treatment in case of any clinical concern

Table 1.4.2: 1 Potential risks, their rationale, and mitigation strategy (cont.)

Potential risks of clinical relevance for this trial	Summary of data, rationale for the risk	Mitigation strategy
Investigational Medicinal Product: Empagliflozin		
DKA	Rare but severe event which can be life-threatening and requires urgent hospitalization; Insulin deficiency might lead to ketoacidosis which could be life-threatening if not recognized and appropriately treated.	DKA is of particular concern for prospective safety monitoring and safety assessment within this trial.  All patients in this trial will be made aware of this risk and be instructed not to reduce their insulin dose below Investigator recommendations.  Investigators should also differentiate deteriorating ketosis/DKA from any mild to moderate increase of ketones expected from the mechanism of action of empagliflozin, especially in the fasted state (e.g., in the morning).
Volume depletion	Based on the mode of action of SGLT-2 inhibitors, osmotic diuresis may lead to a modest decrease in blood pressure and dehydration.	Carefully monitor the volume status and electrolytes (e.g. blood pressure measurements, and laboratory tests including haematocrit);  Patients will be requested to drink plenty of fluids as a precautionary measure.
Hypoglycemia	Because of the mechanism of action of empagliflozin, the risk of hypoglycemic episodes is considered to be low. However, with empagliflozin in combination with insulin, the risk of hypoglycemia may be increased compared to the treatment with insulin alone.	Symptoms attributed to hypoglycemia as well as glucose levels will be closely monitored in the trial.

Table 1.4.2: 1

Potential risks, their rationale, and mitigation strategy (cont.)

Potential risks of clinical relevance for this trial	Summary of data, rationale for the risk	Mitigation strategy
Investigational Medicinal Product: Empagliflozin		
Urinary tract infection (UTI)	
Based on the mode of action of SGLT-2 inhibitors, the incidence of UTI may increase. The pooled analysis of UTI showed that, in general, empagliflozin 10 and 25 mg had similar frequencies of UTIs as placebo. Although rare, urosepsis was reported for more patients treated with empagliflozin than placebo, but there was no increase in frequencies for overall complicated urinary tract infections, including pyelonephritis. The frequency of UTIs leading discontinuations of study drug was 0.6% with both empagliflozin groups compared to 0.3% in the placebo group.
	Symptoms attributed to UTI will be closely monitored in the trial. UTI should be documented as an AE and appropriate therapy should be initiated.
Drug-induced liver injury (DILI)	Rare but severe event, thus under constant surveillance by sponsors and regulators.	Timely detection, evaluation, and follow-up of laboratory alterations in selected liver laboratory parameters to ensure patients' safety.
Trial procedures		
Commonly experienced in association with blood sampling		The amount of blood taken during the whole course of the trial is not believed to be excessive and is associated with the standard of care for the patients.

#### Risk evaluation in relation with COVID-19

Patients with serious underlying medical conditions such as T2D are at higher risk for severe illness from coronavirus disease 2019 (COVID-19). Therefore, in case of local high risk of

COVID-19 infection, on-site visits may not be carried out. In the event of restriction to visit the investigator site, a remote visit can be performed. This change is meant to keep the integrity of the trial and it will not affect the assessment of benefit-risk of empagliflozin.

There is no indication that empagliflozin may increase the risk of COVID-19 infection. As with any acute illness, empagliflozin use / treatment during COVID-19 infection has the potential to increase the risk of diabetic ketoacidosis. The risk of diabetic ketoacidosis in case of acute illness is adequately addressed in the IB and in the patient information and consent form.

In case of a confirmed COVID-19 infection, trial treatment will be discontinued (see [Section 3.3.4.1](#)).

#### **1.4.3      Discussion**

All patients taking part in the trial may derive general medical benefit from careful and close monitoring by medical personnel during the study. Safety will be ensured by monitoring the patients for AEs both clinically and by laboratory testing and by the HBGM. Patients who are not adequately controlled, as evidenced by a confirmed high glucose value (refer to [Section 4.2.1](#)), will receive rescue therapy to ensure their safety or will be excluded from further study participation. The patient will continue to receive standard therapy throughout and the trial medication will be given in addition to this. Therefore they will continue to receive appropriate treatment.

Given the good safety profile in the toxicity studies of empagliflozin and the good tolerability seen in the human studies so far, the careful monitoring to be conducted during the study visits, and the blood glucose monitoring to be performed by the patients at home during the study, the sponsor considers the risks for the participating patients will be minimised and justified when compared with the potential benefits from this trial.

## **2. TRIAL OBJECTIVES AND ENDPOINTS**

The objective of the current study is to investigate the efficacy and safety of Empagliflozin (10 mg or 25 mg, administered orally, once daily) compared to placebo given for 24 weeks in combination with stable insulin with or without up to two oral antidiabetic drugs in Chinese patients with T2DM with insufficient glycemic control.

### **2.1 MAIN OBJECTIVES, PRIMARY AND SECONDARY ENDPOINTS**

#### **2.1.1 Main objectives**

To determine the efficacy and safety of Empagliflozin added to stable insulin in Chinese patients with type 2 diabetes.

#### **2.1.2 Primary endpoint(s)**

The primary endpoint is the change from baseline in glycosylated haemoglobin A1c (HbA1c) after 24 weeks of treatment. Throughout the study protocol, the term "baseline" refers to the last observed measurement prior to administration of any randomised study drug.

[figure not shown]

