#### 4.1.3 Method of assigning patients to treatment groups

When a patient is confirmed eligible for entry into the randomised double-blind treatment period, treatment assignment will be by means of a third-party phone/web-based randomisation at Visit 3. This will involve the use of interactive response technology (IRT). To facilitate the use of the IRT, the Investigator will receive an IRT manual including all necessary instructions for using the IRT. A copy of the manual will be available in the ISF.

After the assessment of all in- and exclusion criteria, each eligible patient will be randomised to treatment groups of Empagliflozin film-coated tablet 10 mg, 25 mg or placebo for Empagliflozin tablet according to a randomisation plan in a 1:1:1 ratio at Visit 3 via Interactive Response Technology (IRT). The randomisation will be stratified by HbA1c (< 8.5% vs. ≥ 8.5%) as determined from the blood sample taken at Visit 1 and background medication (Insulin alone or Insulin+OAD). For further details please refer to [Section 7.5](#).

Note that the medication number is different from the patient number (the latter is generated during screening via the IRT System). The assigned medication number will be entered in the eCRF, and the corresponding medication kit should be given to the patient. Using this procedure, relevant parties will be blinded to the treatment group assignment.

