## **5. ASSESSMENTS**

### **5.1 ASSESSMENT OF EFFICACY**

#### HbA1c

Blood samples for the determination of HbA1c at the central laboratory will be taken at all the visits except Visit 2, the blood sample can be taken at any time during the visit. For the determination of HbA1c, 3 mL of blood will be collected. The samples will be analysed at a central laboratory having a National Glycohaemoglobin Standardization Program (NGSP) Level I certificate. Further details about sample handling, shipment, and assay procedures can be found in the ISF (Lab manual).

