#### **7.2.2 Primary endpoint analyses**

The primary endpoint in this trial is the change in HbA1c (in unit of %) from baseline after 24 weeks of treatment. The baseline HbA1c refers to the last HbA1c assessment prior to the administration of any randomized study drug and not to the HbA1c assessment used for the stratification in the randomisation.

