6.7 BASELINE, TIME WINDOWS, AND CALCULATED VISITS

With regard to efficacy and safety endpoints, the term “baseline” refers to the last observed measurement prior to administration of any randomised study medication.

Measurements taken prior to the first intake of randomised study medication will be considered pre-treatment values. Pre-treatment values will be assigned to a visit according to the nominal visit number as recorded on the eCRF or as provided by the laboratory.

In general, the date and clock time of the first drug administration will be used to separate pre-treatment from on-treatment values; Measurements taken after the first intake of randomised study medication will be considered on-treatment values if they have been obtained up to end of the parameter specific follow-up period as defined in [Table 6.7:1](#) below and will be assigned to the randomised study medication for efficacy analyses and to the first study medication taken for safety analyses.

Proprietary confidential information © 2021 Boehringer Ingelheim International GmbH or one or more of its affiliated companies

Table 6.7:1 Endpoint specific follow-up period for the assignment to treatment phase

Endpoint	Last day of assignment to treatment phase (days after study medication stop date)
Efficacy	
HbA _{1c}	7
FPG	1
Body weight	1
Blood pressure (systolic, diastolic)	1
PPG	1
MDG	1
C-peptide	1
Biomarkers of insulin resistance and secretion	1
Waist circumference	7
Safety	
Adverse events	7
Safety laboratory measurements	3
Pulse rate	1

Measurements taken after the end of the endpoint specific follow-up period and after the last intake of study medication will be considered post-treatment values.

On-treatment efficacy and safety measurements will be assigned to visits based on time windows around the planned visit dates. These time windows are defined based on the planned number of days after the date of first administration of study medication (see [Table 6.7:2](#)).

Proprietary confidential information © 2021 Boehringer Ingelheim International GmbH or one or more of its affiliated companies

Table 6.7:2 Time windows for on-treatment efficacy measurement scheduled for each on treatment visit

Visit number	Visit label	Planned days	Time window (actual days on treatment)	
			Start	End ^A
3	Baseline	0	NA	1 ^B
4	Week 4	28	2	42
5	Week 8	56	43	70
6	Week 12	84	71	105
7	Week 18	126	106	147
8	Week 24/EOT	168	148	Study medication stop date + X days

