7.5.2.2 Change from baseline in body weight, SBP, DBP and FPG

The MMRM models constructed for the primary endpoint will also be conducted for continuous secondary endpoints of change from baseline in body weight, SBP, DBP and FPG at week 24. Analyses will be performed on the mITT set (OC). The model will include the baseline value of the corresponding endpoint and its interaction with visit as covariates.

Proprietary confidential information © 2021 Boehringer Ingelheim International GmbH or one or more of its affiliated companies

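### The readable MMRMs for SBP, DBP, FPG and HbA1c adjust for only the last pre-dose value of the endpoint and leave earlier pre-randomisation values unused, a modest and avoidable loss of precision

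*Protocol*

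**What the plan says.** Both documents use one definition. Protocol 2.1.2 states that baseline "refers to the last observed measurement prior to administration of any randomised study drug". SAP 6.7 says that "the term “baseline” refers to the last observed measurement prior to administration of any randomised study medication".

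**Models**

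- The primary MMRM (Protocol 7.2.2.1, SAP 7.4.1) and the pooled-dose MMRM (SAP 7.4.4) contain one baseline HbA1c with its visit interaction, baseline eGFR and background therapy.
- For body weight, SBP, DBP and FPG, SAP 7.5.2.2 reuses the primary model type and adds: "The model will include the baseline value of the corresponding endpoint and its interaction with visit as covariates". Protocol 7.2.3 calls these additional covariates, which suggests that baseline HbA1c stays in those models.

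**Measurements before randomised dosing (Flow Chart)**

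- Vital signs are taken at Visits 1, 2 and 3 (Weeks -3, -2 and 0).
- FPG is taken at Visits 2 and 3.
- HbA1c is taken at Visits 1 and 3. Protocol 5.1 confirms that these samples "will be taken at all the visits except Visit 2".

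**Stratification.** Protocol 4.1.3 and 7.4 stratify by Visit 1 HbA1c (<8.5% or ≥8.5%) and by background therapy. Protocol 7.2.2 makes clear that the baseline is not the HbA1c "assessment used for the stratification in the randomisation". Background therapy is a model term; the Visit 1 HbA1c is not, in any model that can be read.

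**The concern.** Single-visit blood pressure and fasting glucose vary from day to day, so one visit's value is a noisy measure of a patient's usual level. Earlier values of the same variable carry further information about that level. They precede randomisation, so using them as covariates cannot bias the treatment comparison, and they will already be in the database. Leaving them out makes the confidence intervals for each dose against placebo somewhat wider than necessary, with 72 patients per arm. The plan states power only for HbA1c, so the precision of SBP, DBP and FPG rests entirely on the analysis model. In addition, one of the two randomisation factors enters the primary model only through a sample taken about three weeks later.

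**Working it through.** **Reproducing the plan's figure.** The inputs from Protocol 7.5 are effect 0.62, SD 1.1 (already labelled covariate-adjusted), two-sided alpha 0.05, 8% censoring and information content 0.4. The noncentral t distribution gives 68 per arm with power 90.4% (plan: 90.3%). Then 68 / (1 - 0.08 × 0.6) = 71.4, rounded up to 72. The plan's figures reproduce.

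**Method.** Let r hold the correlations of the pre-dose values with Week 24, and R the correlations among the pre-dose values. The residual variance is 1 - r'R⁻¹r. With Visit 3 alone it is 1 - r3². All correlations below are assumptions, because the documents give none.

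**SBP and DBP, three visits against one**

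With a common correlation ρ between the pre-dose visits, r'R⁻¹r = [Σr² - ρ(Σr)²/(1+2ρ)]/(1-ρ).

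- *Older readings predict less well.* Visit 2 is set midway between Visits 1 and 3.
  - r = 0.50, 0.475, 0.45 and ρ = 0.60: [0.678125 - 0.6 × 2.030625/2.2]/0.4 = 0.3108. Residual 0.6892 against 0.75, a cut of 8.1% (CI 4.1% narrower).
  - r = 0.60, 0.57, 0.54 and ρ = 0.75: [0.9765 - 0.75 × 2.9241/2.5]/0.25 = 0.3971. Residual 0.6029 against 0.64, a cut of 5.8% (CI 2.9% narrower).
  - Similar decaying patterns give about 5% to 8%. Pairing r3 = 0.50 with ρ = 0.75 lowers the cut to 3.4%.
- *All correlations equal.*

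| Common correlation | Residual, 1 visit | Residual, 3 visits | Variance cut | CI narrower by |
|---|---|---|---|---|
| 0.5 | 0.750 | 0.625 | 16.7% | 8.7% |
| 0.6 | 0.640 | 0.509 | 20.5% | 10.8% |
| 0.7 | 0.510 | 0.388 | 24.0% | 12.8% |

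In the first decaying pattern, using the mean of Visits 1 and 2 as one covariate captures 8.0% of the available 8.1%.

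**FPG, two visits against one**

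The proportional cut from adding an earlier value with correlation r1 is (r1 - ρ·r3)²/[(1-ρ²)(1-r3²)].

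- r3 = 0.50, r1 = 0.45, ρ = 0.60: 0.15²/(0.64 × 0.75) = 4.7%.
- The same with ρ = 0.65: 0.125²/(0.5775 × 0.75) = 3.6%.
- These figures leave baseline HbA1c out of the model. Suppose it is in, correlating 0.5 to 0.7 with pre-dose FPG and 0.4 to 0.5 with Week 24 FPG. Applying 1 - r'R⁻¹r with and without Visit 2 then gives cuts of 0.9% to 4.1% over that grid, at most 3.1% in all but one corner.
- Equal correlations of 0.4, 0.5 and 0.6, without HbA1c, would give 8.2%, 11.1% and 14.1%.

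**HbA1c, two values against one (same formula)**

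- ρ = 0.90, r1 = r3 = 0.60: 0.06²/(0.19 × 0.64) = 3.0%, power 91.2%.
- ρ = 0.85, r3 = 0.60, r1 = 0.589: 0.079²/(0.2775 × 0.64) = 3.5%. SD 1.1 × √0.965 = 1.081, power 91.3%.
- r1 = ρ·r3, where Visit 1 predicts Week 24 only through Visit 3: cut 0, power unchanged.
- Larger gains need more favourable inputs. Equal prediction at ρ = 0.85 gives 0.09²/0.1776 = 4.6% (power 91.6%). At ρ = 0.80 with r1 = r3 = 0.60 it gives 6.2% (power 92.1%).

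**Price of the extra term.** One more coefficient acting at Week 24 inflates the variance by roughly 1/200 = 0.5%. The SBP and DBP gain clearly exceeds this, and the FPG gain generally does. The HbA1c gain may not.

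**The case against.** The strongest reply is that this is a preference about efficiency. The two documents agree on baseline, the models can be run as written, and the primary endpoint has its 90% power on an SD that is already covariate-adjusted. There are also reasons to prefer Visit 3. Protocol 3.2 gives the run-in the task of stabilising glucose parameters other than HbA1c, and the Visit 2 FPG precedes it. Most Visit 1 procedures may be done in the fed state (Protocol 6.2.1). Blood pressure is read three times at each time point, so its baseline does not rest on one reading. SBP, DBP and FPG lie outside the confirmatory hierarchy.

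Most of this stands as a limit on size. The run-in and fed-state points may make earlier values less predictive, which is why the decaying patterns are the better guide. Repeat readings reduce same-day noise but not variation between visits.

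A reader might draw three stronger conclusions that the documents do not support:

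- **That the primary analysis is biased or invalid because a stratification factor is missing.** Continuous baseline HbA1c with its visit interaction is in the model, taken about three weeks after the stratifying sample, and so is background therapy. The omitted part is small.
- **That blood pressure intervals are 9% to 13% wider than they need be.** This requires readings two to three weeks apart to correlate no better than readings 24 weeks apart.
- **That every model discards data.** The 2-hour PPG has only one pre-dose visit. Some SAP sections are absent from the public copy, so the statement covers readable models only.

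**Conclusion.** The point holds as a low-cost gain in precision for three secondary endpoints and, marginally, the primary. The direction is sure, since adding a predictive pre-randomisation covariate does not raise the large-sample residual variance. The size rests wholly on assumed correlations:

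- **SBP and DBP:** about 5% to 8% less Week 24 residual variance if older readings predict less well, with 17% to 24% as the ceiling under equal correlations of 0.5 to 0.7. This is the strongest part.
- **FPG:** roughly 1% to 5% with decaying correlations, and less once baseline HbA1c is in the model.
- **HbA1c:** about 0% to 3.5%, with power at most about 91% against the stated 90.3%. The reason to act here is agreement with the stratified randomisation rather than power.

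Body weight is also measured at Visits 1 and 3. It is left out because the Visit 1 weight need not be fasting (Protocol 5.1).

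**What to change.** Before unblinding:

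1. Keep the Visit 3 value as the reference for change from baseline, so that endpoints and treatment contrasts are unchanged.
2. In SAP 7.5.2.2, add the mean of the available Visit 1 and Visit 2 SBP (or DBP), with its visit interaction, as a second covariate. Optionally add the Visit 2 FPG in the same way to the FPG model, and state whether baseline HbA1c remains in these models.
3. In SAP 7.4.1 and 7.4.4, add the Visit 1 HbA1c with its visit interaction, or its <8.5% / ≥8.5% stratum. Use the central laboratory value, in line with SAP 7.1.
4. State a rule for a missing earlier value, for example single imputation from pre-randomisation data, blind to treatment. FPG and HbA1c each have only one earlier value, so there is no other to substitute. Also cover a missing Visit 3 value: baseline then falls back to an earlier value, and for FPG and HbA1c the two covariates coincide.
5. Declare the change in SAP section 4, which now reports no departures, because Protocol 7.2.2.1 and 7.2.3 list the covariates.

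The cost is one extra covariate per model with its visit interaction (five coefficients over Visits 4 to 8), and a declared departure from the protocol model. No new data are needed.

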#### **2.1.3 Secondary endpoint(s)**

[figure not shown]
Secondary efficacy endpoints are:

- Percentage of patients with HbA1c<7.0% after 24 weeks of treatment
- Change in body weight from Baseline to week 24
- Change in systolic blood pressure (SBP) from baseline to week 24
- Change in diastolic blood pressure (DBP) from baseline to week 24
- Change in Fasting Plasma Glucose (FPG) from baseline to week 24
- Change in 2-hour Post-prandial Glucose (PPG) from baseline to week 24

Secondary safety endpoints are:

- Occurrence of hypoglycemic events
- Occurrence of adjudicated diabetic ketoacidosis (DKA) events

### 3. DESCRIPTION OF DESIGN AND TRIAL POPULATION

#### 3.1 OVERALL TRIAL DESIGN AND PLAN

This randomised, double-blind, multi-center, placebo-controlled, parallel group study compares Empagliflozin (10 mg or 25 mg) to placebo as add-on therapy to stable insulin with or without up to two oral antidiabetic drugs. The trial design is illustrated in [Figure 3.1: 1](#).

In total, approximately 216 patients with T2DM who meet the entry criteria are planned for inclusion in this trial. The randomised treatment will be double-blind between Empagliflozin and placebo (i.e. each patient will receive one of two active treatments of Empagliflozin or placebo matching Empagliflozin).

Patients already on treatment with insulin with or without other OADs enter a 2-week open-label placebo run-in period. Patients who successfully complete the run-in period and who still meet the inclusion /exclusion criteria will be randomised to the 24-week treatment period of the study.

An independent external Clinical Event Committee (CEC) will be established to adjudicate centrally and in a blinded fashion events suspected of DKA (for further details see [Section 5.2.6.1.4](#)). The CEC will evaluate whether pre-specified criteria for adjudication endpoints are met.

For any events that qualify for adjudication, study sites will be asked to provide clinical documentation such as laboratory values, discharge summaries etc. to support the external event adjudication.

The tasks and responsibilities of the CEC will be specified in a charter. The CEC will maintain the adjudication results in writing.

Certain hepatic events will be adjudicated by external independent experts for severity and causal relationship with the trial medication in a blinded fashion. The events which will be reviewed are defined in a charter for hepatic events. Events may either be defined by abnormal laboratory values and/or relevant adverse events or both. For example, assessments will be made for hepatic injury events, including liver enzyme elevations.

For qualifying events, relevant source documents generated from any medical evaluations of these events will be requested including laboratory values, histological analysis, results of ultrasound, CT, MRI, scintigraphy, hospital discharge letters, and medical reports from other physicians. All evaluations will be performed in a blinded fashion. The assessments will be analysed based on empagliflozin data combined from multiple trials (i.e. on project level).

[figure not shown]

Figure 3.1: 1 Trial design

